# 8. Adverse Event Reporting.

As outlined in the DSMP below, the IRB will be notified of reportable events within one week of the event by the study PIs. Adverse events will also be reported to the NINR Program Officer within one week of the event.

# 9. Data Safety and Monitoring Plan (DSMP)

A safety monitoring committee (SMC) will be established to monitor the study. This committee will be composed of:

- Chair: [name], RN, PhD, Professor, Associate Dean for Academic Advancement, School of Nursing, Emory University
- Members: [name], Rn, PhD, Professor, Associate Dean for Research, School of Nursing, Emory University

[name], Assistant Professor, Biostatistics, School of Nursing, Emory University

The SMC will meet with the PIs **annually** or as needed to review conduct of the trial, including informed consent procedures, accrual, recruitment, and retention, violations in protocols, adverse events, breaches in confidentiality, or other data related to the protection of human subjects. They will also review and make

recommendations on the data transfer and warehousing procedures. The primary role of the SMC will be to ensure data integrity and the safety of participants. They will have the power to recommend conclusion of the trial and provision of the intervention to the control group if significant improvements in outcomes occur. They will also have the power to recommend conclusion of the trial if significant risks develop, or if the project is unlikely to conclude successfully.

The first meeting will occur at the beginning of the trial and at this meeting the committee will review and make recommendations about the consent procedures, and situations within which confidentiality may be broken, such as if a participant becomes a threat of physical harm to self or others. In addition, study protocols, recruitment, retention procedures will be examined for timeliness, practicality, safety, and protection of human subjects. Any recommendations that emanate from monitoring activities will be communicated to the NINR within 7 days if the human subjects research or DSM plan is changed prior to implementation of the trial for approval prior to initiation.

At the subsequent regular annual meetings, the SMC will review:

- a. adherence to the goals for recruitment and retention;
- b. adherence to the study protocols;
- c. cumulative data for evidence of study related adverse events;
- d. quality, completeness, and timeliness of the data collected;
- e. factors that could affect the outcome or compromise participant/data confidentiality;
- f. other factors outside the study (e.g., therapeutic developments, agency related policies) that could impact the safety of participants or the ethical conduct of the study.

In general, recommendations the SMC may make include:

- a. continue the study without change;
- b. modifications to the study protocol;
- c. suspension or early termination;
- d. alternative approaches to consider (e.g., if there is a failure to accrue participants as anticipated).

All adverse events that occur during the study will be sent to the SMC chairperson, who will distribute them to the other members of the committee. The relatedness of the event to the study would be provided at the time of presentation of the information. In addition the Emory University IRB and the NINR Program Officer will be notified within one week of the event by the study PIs. The SMC chairperson will transmit an annual report of its findings to the funding agency, the local IRB, and the study PIs.

In compliance with the NINR DSM Policy on Extramural Clinical Trials 2014, the PIs will report the following to the NINR:

- a. Unanticipated problems or unexpected serious adverse events that may be related to the study protocol.
- b. IRB-approved revisions to the study protocol that indicate a change in risk for participants.
- c. A summary of recommendations made by the SMC and an action plan for response.
- d. Notice of any actions taken by the IRB or regulatory bodies regarding the research and any responses to those actions.

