**Process Evaluation:** Documentation of the delivery of the intervention will be provided through research assessment visits and telephone calls, plus participant evaluation of the group sessions. The Fitbits, polar HR monitor data, step logs, and pedometer data will be monitored during the group sessions and telephone calls and collected at each scheduled study visit. Research staff performing the intervention will use a quality indicator form to record their delivery of specific aspects of the intervention each session, difficulties encountered, and questions or issues raised by participants. These data will be entered into the database in the form of field notes which will be text-analyzed for themes. Participants will also be asked to evaluate the benefits of the sessions as well as make suggestions for improvement.

Attention Control (AC) Arm: *Let's Flex Program*. As delineated in the figure above, all study assessments will also be completed by the Let's Flex attention control condition participants. Content of the sessions and all contact will be on flexibility and stretching and will provide control for the possible confounding variable of receiving an exercise program and is also expected to reduce attrition and patient dissatisfaction and to better ensure concealment of group allocation. These time-equivalent flexibility/stretching movements have been previously piloted and were well received, but were not strong enough to influence cardiovascular or biomarker outcomes. For ethical and cardiovascular health reasons, the AC group will be advised to exercise, but will not be provided with education on exercise, nor receive an exercise prescription. The AC group will only be provided with stretching information. Let's Flex participants will document adherence to the flexibility protocol on a Let's Flex log that will be reviewed during groups/visits. Assessments at each time point indicated in tables 4-7 will also be completed with the AC group identical to the intervention group.

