**Risks/Discomforts.** Potential Risks are expected to be minimal since participants will be referred from and/or attending health clinics under the care of an infectious disease physician and receiving optimal medication therapies for HIV. We will conduct a brief history and physical examination before aerobic capacity tests (modified Balke or Bruce) are conducted. If a participant becomes fatigued and does not wish to continue, they will be rescheduled for an additional appointment to complete the remainder of the tests.

The risks associated with administering the modified Balke or Bruce treadmill tests are anticipated to be minimal but may include: atrial and ventricular arrhythmias, sudden death, angina, adverse blood pressure changes (high or low), dyspnea, fatigue, falling, orthopedic/musculoskeletal injuries and complaints, dizziness, and electrocardiographic evidence of ischemia. We will administer the modified Balke or Bruce, a symptom limited treadmill test, at the Clinical Research Network (CRN) by an exercise physiologist and under the supervision of a trained health care provider. Before the exercise testing, each participant will walk for 2 minutes to warm up and to avoid potential muscle soreness. Emergency equipment, medical and nursing staff are immediately available should the participant have any adverse response. A continuous electrocardiogram and blood pressure readings every 1 minute will be recorded. If ST elevation or multiple ventricular ectopy

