The potential risks associated with the Let's Move intervention are anticipated to be minimal. Any potential cardiovascular (CV) events that poses risk to the participant is anticipated to be detected during the modified Balke or Bruce maximal treadmill test. In addition, the duration of walking will be limited to 30 minutes during the first 2 weeks and at an intensity level (60%) that is not likely to result in any adverse CV events; if necessary participants can rest as needed until the 30 minute duration of walking is completed. Participants will wear a Polar HR monitor or a Fitbit so that HR and intensity level can be closely monitored. Participants in the study will be provided with detailed instructions on self-monitoring HR, BP and symptoms associated before, during and after walking. Each participant will be provided with a target heart rate range to stay within during the study period. Participants will be instructed to wear the Polar HR monitor or Fitbit during each exercise session. The participants will take their HR, and BP (if machine available) and weight prior to and after each walking session and record it in their walking calendar. Participants will be instructed to call the research staff if their BP or HR is outside their normal range. If participants are symptomatic, experience increased shortness of breath over the previous 24 hours, they will be instructed not to exercise. The participants will be instructed to take their medications as usual prior to exercise and instructed on proper attire for exercising. Demonstrations and return demonstrations of the Polar HR monitor or Fitbit will ensure they know how to wear the monitors (Polar HR monitors specifically around the chest) as well as trouble shoot when either of the monitors does not display correctly. They will be instructed that if their HR approaches within 5-10 beats of the target HR range to slow the walking pace down. In addition, they will be instructed to monitor their RPE using the Borg 6 to 20 scale, and to keep their RPE at 12-13 during the initial weeks and to gradually progress with instructions to 15 as stipulated in the protocol. Participants in the intervention groups will be advised to carry a cell phone when they walk at home in the event of an emergency or sudden event. Specifically, participants will be instructed to slow their pace if their HR increases to near THR as previously noted or if they become short of breath. Participants who have ischemic heart disease and prescribed nitroglycerin (NTG) will be instructed to carry their NTG with them during each walking sessions. If chest pain occurs during exercise, the participants will be told to stop exercising and to take a NTG as directed by their cardiologist. The participant will also be instructed if the chest pain continues to sit down and to call a relative or friend and to take another NTG if the chest pain does not subside. If the chest pain continues and is not relieved by NTG within 10 minutes they will be instructed to call 911. If the participant becomes moderately to severely dyspneic where they cannot talk while walking they will be instructed to stop walking until the dyspnea subsides. If the dyspnea continues once they have stopped walking for several minutes they will be instructed to call a relative or friend; if not dissipated they will be instructed to go the nearest emergency room. If a participant becomes dizzy while walking they will be asked to sit down and to get up slowly once the dizziness passes. In our previous and ongoing work with heart failure patients and family caregivers, there were no adverse events reported for walking at the 60-70% intensity levels using a very similar protocol. If symptoms are present at current intensity level or duration of walking the participant will not be progressed until exercising at current level with RPE at 15 or below for 45 minutes. This will better ensure the participant is not progressed too rapidly.

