#### 7. Statistical Analysis.

**Phase 3 Data Analysis**. The objectives of phase 3 are to: 1) maintain data files; 2) evaluate study outcomes; and 3) disseminate study results and project materials.

**Data management** Procedures for data management and monitoring will be initiated during the start-up phase. The project coordinator will coordinate the organization and processing of forms, and schedule and implement checks of data quality and completeness. Data from the ACASI files will be saved in the database. Data will be backed up on a regular basis to prevent loss of data. Data will be transferred electronically from the sites to a secure password protected network drives where it will be checked and downloaded. A data-checking plan based on each questionnaire will be used to look for suspicious entries. Data monitoring will be merged as necessary to answer the research questions. [name] will oversee the final quality assurance/quality control data reviews. She will design and conduct the statistical analyses; assist as needed with designing research forms and data entry; and collaborate with the investigators on analysis and interpretation. We have successfully used these procedures in our research projects.

**Sample size and Power Calculation.** For longitudinal analyses of cognitive functioning and biological measures (Aims 1 and 2), our sample size provides adequate power (80%) to detect effect sizes of 0.37 or larger at alpha=0.05. Our ongoing study (Caregiver Stress study) showed that between-group effect sizes related to exercise vs. AC groups are on the order of 0.5 to 0.8 for physiological, physical and psychological functions.

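### Adverse events are collected differently in the two arms and are never summarised by arm, so harms of Let's Move cannot be reliably compared with Let's Flex

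*Combined protocol and SAP*

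**What the plan says.** **Routing and review (sections 8 and 9).** "All adverse events that occur during the study will be sent to the SMC chairperson", who passes them to the other members. Relatedness goes with the report: "The relatedness of the event to the study would be provided at the time of presentation of the information". The SMC's general remit lists "violations in protocols, adverse events, breaches in confidentiality" without a relatedness condition. Item c of its annual review list is "cumulative data for evidence of study related adverse events". The SMC may recommend ending the trial if significant risks emerge. Section 8 has adverse events reported to the funder's programme officer within one week.

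**Foreseen harms (section 5, Risks/Discomforts).** For the treadmill test the protocol lists arrhythmias and sudden death among others, and goes on to "dyspnea, fatigue, falling, orthopedic/musculoskeletal injuries and complaints, dizziness, and electrocardiographic evidence of ischemia". For home walking it gives instructions on chest pain, dyspnoea and dizziness.

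**Capture in Let's Move (same subsection).** Participants record heart rate, weight and, if they have a machine, blood pressure before and after each walk. "Participants will be instructed to call the research staff if their BP or HR is outside their normal range".

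**Capture in Let's Flex.** The Risks/Discomforts paragraph for this arm calls the risk minimal and gives no instruction to contact staff. The Attention Control paragraph says "Content of the sessions and all contact will be on flexibility and stretching", and the Let's Flex log documents adherence.

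**Analysis (section 7).** "The objectives of phase 3 are to: 1) maintain data files; 2) evaluate study outcomes", followed by dissemination. The aims analysed are cognition, biomarkers and mediation.

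**The concern.** Let's Move prescribes five home sessions a week through week 58 for sedentary adults aged 50 and over (40 and over in one place in section 5) with cognitive impairment. If it improves cognition, the next question is whether it causes more falls, injuries or cardiac symptoms than stretching. That needs events found in the same way in both arms and set out by arm with a denominator.

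The text provides neither. One arm has a written prompt to report and the other does not, and the staff who deliver each programme know which one it is. An event in a control participant that nobody asks about may never be recorded, and a table produced later cannot restore it. The SMC has the same difficulty during the trial: it may recommend stopping for risk, yet no by-arm harms summary is planned for it.

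**Working it through.** The plan gives no harms figure to reproduce. The check sets the relevant places side by side and then illustrates the direction of the bias.

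**1. Ascertainment by arm, from section 5**

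| Element | Let's Move | Let's Flex |
|---|---|---|
| Heart rate, weight and (if available) blood pressure recorded around sessions | Yes | Not stated |
| Told to call staff for out-of-range blood pressure or heart rate | Yes | Not stated |
| Log or calendar | Step calendar: maximum heart rate, perceived exertion, steps | Log: adherence |
| Group sessions, follow-up calls, visits | Yes | Yes |
| Assessments of Tables 4-7 | Yes | Yes, identical |
| Scheduled adverse-event question at those contacts | None stated | None stated |

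Two details limit the contrast. Let's Move participants are taught to monitor symptoms, but symptoms are not among the items they are said to write down. The instructions on chest pain, dyspnoea and dizziness point to rest, a relative or friend, emergency services or an emergency room, and contain no step for telling the study. Capture is therefore largely passive in both arms. The documented difference is the session recording and the one call-in instruction.

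**2. Contacts already available.** Telephone monitoring is weekly from the end of the group sessions to T1, bi-weekly from T1 to T2 and monthly from T2 to T3. Its stated content is progress and barriers. Risks/Discomforts mentions follow-up calls and clinic visits for the attention control as well. A common question thus has a place to go without new contacts.

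**3. Summary by arm.** Section 7 analyses cognition, biomarkers and mediation. Sections 8 and 9 cover notification and committee review. None of them tabulates adverse events by arm.

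**4. Direction of the bias, under assumed values.** With the same true risk in both arms,

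apparent risk ratio = capture in Let's Move / capture in Let's Flex.

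The documents give no capture probabilities or event risks. Assume 90% capture in Let's Move:

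- 70% capture in Let's Flex: 0.90 / 0.70 = 1.29
- 50% capture in Let's Flex: 0.90 / 0.50 = 1.80
- equal capture: 1.00

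With an assumed true risk of 10% and arms of 132 and 68, expected reports are 132 × 0.10 × 0.90 = 11.9 against 68 × 0.10 × 0.70 = 4.8, or 68 × 0.10 × 0.50 = 3.4. These values show direction only.

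**5. Estimate or test?** For an assumed risk of 10% in Let's Flex and 20% in Let's Move, a two-sided 5% comparison of proportions has power of about 43% with 132/68, and about 34% with 107/53 if 107 is taken as Let's Move. A non-significant test would say little, so estimates with intervals are the better summary.

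**6. Denominators.** The Abstract and section 4 give 132 Let's Move and 68 Let's Flex. The design paragraph of section 5 gives 107 Let's Flex and 53 Let's Move, the reverse of the 2:1 direction in section 4.

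**The case against.** The strongest reply is that safety oversight is broader than item c suggests and that controls are not cut off from the study. Much of this stands.

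- **A reader might infer that the SMC sees only study-related events, or only isolated reports.** The text does not support that. All events go to the chair and members, relatedness is a label and not a filter, the general remit is unfiltered, and item c is itself a review of cumulative data. It can fairly be read as a search of all the data for signs of study-related harm.
- **A reader might infer that controls have no way to report.** Participants receive project office telephone numbers at the baseline visits, with no restriction by arm. Controls have groups, calls and visits. The treadmill test with cardiologist-read ECG and the symptom and pain questionnaires are scheduled in both arms. The quality indicator form leaves room for difficulties and issues raised by participants. The sentence limiting control contact to stretching describes programme content and does not forbid recording an event. Consent pages are not in the copy reviewed, so nothing is assumed about what they say on reporting injury.
- **A reader might infer that harms of exercise would be hidden or never reported.** Unequal capture of this kind works the other way, towards an apparent excess in Let's Move.
- **A reader might infer that the damage is wholly irreversible, or that 2:1 raw counts will mislead.** No raw-count comparison is planned, denominators can be added later, and events judged unrelated remain on file. Only events never elicited are lost.

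The reply leaves two gaps open: no common scheduled question, and no summary by arm.

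**Conclusion.** The point holds in limited form. All adverse events reach the SMC, but the written means of detecting them differ by arm, neither arm has a scheduled adverse-event question, and no harms summary by arm is planned. As written, the trial cannot give a reliable comparison of the harms of Let's Move with those of Let's Flex.

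The likely direction is an overstated excess in the exercise arm. The size cannot be estimated from the documents: the ratios of 1.29 and 1.80 rest entirely on assumed capture. The conclusion assumes that staff follow the text as written and that no separate manual or form already sets a common question. It does not touch the cognitive or biomarker analyses, and it amounts to a cheap improvement.

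**What to change.** 1. **Same question in both arms.** At every existing follow-up call and at T1, T2 and T3, ask one fixed, scripted adverse-event question, with prompts for falls, injuries and cardiac symptoms. Record whether each event came from this question or from a spontaneous call, so that the comparison can rest on the source common to both arms. The existing participant safety instructions need no change for this.
2. **A table by arm in section 7 and for the SMC.** List all adverse and serious adverse events by randomised arm regardless of relatedness: participants with at least one event, person-time from randomisation, and a rate ratio or risk difference with 95% confidence interval. Present estimates, not a test. State how an adverse event and a serious adverse event are defined, which the protocol does not do at present. Reconcile the arm sizes first (132/68 against 107/53 with labels reversed).
3. **Clarification in section 9.** Align item c with the routing sentence, so that the cumulative review covers all adverse events by arm with denominators.

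Cost: one script, one table and one edited line, a few minutes per contact, and more minor events recorded.
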